### **Clinical Laboratory Tests**

Laboratory data will be summarized by type of laboratory test (eg, hematology, clinical chemistry). Selected laboratory parameters will be summarized by treatment groups. Common Terminology Criteria (CTC) will be used to identify abnormal laboratory test results, and the incidence and severity of abnormal laboratory parameters (hematology and chemistry) will be summarized by treatment group.

In addition, a listing of participants with Grade 2 or higher laboratory test results (based on the CTC criteria) will also be provided.

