### **5.6.3. Additional Safety Assessments**

#### **5.6.3.1. Clinical Laboratory Tests**

Clinical laboratory tests will be displayed for the participants included in the safety analysis set.

Descriptive statistics of change from baseline through Week 36 will be summarized for selected chemistry, and hematology tests and displayed by intervention group.

- **Hematology** will include but are not limited to the following: Basophils, Eosinophils, Hemoglobin, Lymphocytes, Monocytes, Neutrophils, Platelets, WBC, CRP and ESR.
- **Chemistry** will include but are not limited to the following: ALT, AST, Albumin, Alkaline Phosphatase, Bicarbonate (CO2), Calcium, Chloride, Creatinine, GGT, Glucose, Potassium, SGOT, SGPT, Sodium, Total Bilirubin, Total Protein, Urea Nitrogen.

Applicable laboratory results will be graded according to National Cancer Institute's Common Terminology Criteria for Adverse Events (NCI-CTCAE). Participants with toxicity grades  $\geq 2$  will be listed.

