## **6.9. Appendix 10 Laboratory Toxicity Grading**

The grading scale use for lab assessments is based on ‘Common Terminology Criteria for Adverse Events (CTCAE) v5.0’.

If a laboratory value falls within the grading as specified below but also within the local laboratory normal limits, the value is considered to be normal and will be reset to grade 0.

Pre-baseline measurements will use the same grading ranges as applied to baseline measurements. In case a test has two sets of ranges – one for baseline normal and one for baseline abnormal, the one for baseline normal will be applied for all measurements taken pre-baseline and on baseline.

CTCAE Term	Grade 1	Grade 2	Grade 3	Grade 4	Janssen implementation notes
Blood and lymphatic system disorders					
Anemia	Hemoglobin (Hgb) <LLN - 10.0 g/dL; <LLN - 6.2 mmol/L; <LLN - 100 g/L	Hemoglobin (Hgb) <10.0 - 8.0 g/dL; <6.2 - 4.9 mmol/L; <100 - 80g/L	Hemoglobin (Hgb) <8.0 g/dL; <4.9 mmol/L; <80 g/L; transfusion indicated	Life-threatening consequences; urgent intervention indicated	Clinical signs and symptoms are not taken into consideration for grading.
Leukocytosis	-	-	>100,000/mm  ; >100 x 10e9 /L	Clinical manifestations of leucostasis; urgent intervention indicated	Clinical signs and symptoms are not taken into consideration for grading; Added ranges in SI unit (x 10e9 /L)
Investigations					
Activated partial thromboplastin time prolonged	>ULN - 1.5 x ULN	>1.5 - 2.5 x ULN	>2.5 x ULN; bleeding	-	Clinical signs and symptoms are not taken into consideration for grading.
Alanine aminotransferase increased	>ULN - 3.0 x ULN if baseline was normal; 1.5 - 3.0 x baseline if baseline was abnormal	>3.0 - 5.0 x ULN if baseline was normal; >3.0 - 5.0 x baseline if baseline was abnormal	>5.0 - 20.0 x ULN if baseline was normal; >5.0 - 20.0 x baseline if baseline was abnormal	>20.0 x ULN if baseline was normal; >20.0 x baseline if baseline was abnormal	Ranges defined for “abnormal baseline” are applied only if baseline > ULN. If baseline < LLN, then ranges for “normal baseline” are applied.

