Neutrophil count decreased	<LLN - 1500/mm  ; <LLN - 1.5 x 10  /L	<1500 - 1000/mm  ; <1.5 - 1.0 x 10  /L	<1000 - 500/mm  ; <1.0 - 0.5 x 10  /L	<500/mm  ; <0.5 x 10  /L	Both Neutrophils and segmented neutrophils are graded using these criteria.
Platelet count decreased	<LLN - 75,000/mm  ; <LLN - 75.0 x 10  /L	<75,000 - 50,000/mm  ; <75.0 - 50.0 x 10  /L	<50,000 - 25,000/mm  ; <50.0 - 25.0 x 10  /L	<25,000/mm  ; <25.0 x 10  /L	
Serum amylase increased	>ULN - 1.5 x ULN	>1.5 - 2.0 x ULN; >2.0 - 5.0 x ULN and asymptomatic	>2.0 - 5.0 x ULN with signs or symptoms; >5.0 x ULN and asymptomatic	>5.0 x ULN and with signs or symptoms	“Asymptomatic” ranges are not taken into consideration for grading, i.e. worst case grading is applied.
White blood cell decreased	<LLN - 3000/mm  ; <LLN - 3.0 x 10  /L	<3000 - 2000/mm  ; <3.0 - 2.0 x 10  /L	<2000 - 1000/mm  ; <2.0 - 1.0 x 10  /L	<1000/mm  ; <1.0 x 10  /L	
Metabolism and nutrition disorders					
Acidosis	pH <normal, but $\geq 7.3$	-	pH <7.3	Life-threatening consequences	pH <normal is implemented as pH <LLN. Clinical signs and symptoms are not taken into consideration for grading.
Alkalosis	pH >normal, but $\leq 7.5$	-	pH >7.5	Life-threatening consequences	pH >normal is implemented as pH >ULN. Clinical signs and symptoms are not taken into consideration for grading.

CTCAE Term	Grade 1	Grade 2	Grade 3	Grade 4	Janssen implementation notes
Hypercalcemia	Corrected serum calcium of >ULN - 11.5 mg/dL; >ULN - 2.9 mmol/L;  Ionized calcium >ULN - 1.5 mmol/L	Corrected serum calcium of >11.5 - 12.5 mg/dL; >2.9 - 3.1 mmol/L;  Ionized calcium >1.5 - 1.6 mmol/L;  symptomatic	Corrected serum calcium of >12.5 - 13.5 mg/dL; >3.1 - 3.4 mmol/L;  Ionized calcium >1.6 - 1.8 mmol/L;  hospitalization indicated	Corrected serum calcium of >13.5 mg/dL; >3.4 mmol/L;  Ionized calcium >1.8 mmol/L;  life-threatening consequences	Clinical signs and symptoms are not taken into consideration for grading.

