Hyperkalemia	Potassium >ULN - 5.5 mmol/L	Potassium >5.5 - 6.0 mmol/L;  intervention initiated	Potassium >6.0 - 7.0 mmol/L;  hospitalization indicated	Potassium >7.0 mmol/L;  life-threatening consequences	Clinical signs and symptoms are not taken into consideration for grading.
Hypermagnesemia	Magnesium >ULN - 3.0 mg/dL; >ULN - 1.23 mmol/L	-	Magnesium >3.0 - 8.0 mg/dL; >1.23 - 3.30 mmol/L	Magnesium >8.0 mg/dL; >3.30 mmol/L;  life-threatening consequences	Clinical signs and symptoms are not taken into consideration for grading.
Hypernatremia	Sodium >ULN - 150 mmol/L	Sodium >150 - 155 mmol/L;  intervention initiated	Sodium >155 - 160 mmol/L;  hospitalization indicated	Sodium >160 mmol/L;  life-threatening consequences	Clinical signs and symptoms are not taken into consideration for grading.
Hypertriglyceridemia	Triglycerides 150 mg/dL - 300 mg/dL; 1.71 mmol/L - 3.42 mmol/L	Triglycerides >300 mg/dL - 500 mg/dL; >3.42 mmol/L - 5.7 mmol/L	Triglycerides >500 mg/dL - 1000 mg/dL; >5.7 mmol/L - 11.4 mmol/L	Triglycerides >1000 mg/dL; >11.4 mmol/L;  life-threatening consequences	Clinical signs and symptoms are not taken into consideration for grading.
Hypoalbuminemia	Albumin <LLN - 3 g/dL; <LLN - 30 g/L	Albumin <3 - 2 g/dL; <30 - 20 g/L	Albumin <2 g/dL; <20 g/L	Life-threatening consequences; urgent intervention indicated	Clinical signs and symptoms are not taken into consideration for grading.
Hypocalcemia	Corrected serum calcium of <LLN - 8.0 mg/dL; <LLN - 2.0 mmol/L;  Ionized calcium <LLN - 1.0 mmol/L	Corrected serum calcium of <8.0 - 7.0 mg/dL; <2.0 - 1.75 mmol/L;  Ionized calcium <1.0 - 0.9 mmol/L;	Corrected serum calcium of <7.0 - 6.0 mg/dL; <1.75 - 1.5 mmol/L;  Ionized calcium <0.9 - 0.8 mmol/L;	Corrected serum calcium of <6.0 mg/dL; <1.5 mmol/L;  Ionized calcium <0.8 mmol/L;	Clinical signs and symptoms are not taken into consideration for grading.

CTCAE Term	Grade 1	Grade 2	Grade 3	Grade 4	Janssen implementation notes
		symptomatic	hospitalization indicated	life-threatening consequences	
Hypoglycemia	Glucose <LLN - 55 mg/dL; <LLN - 3.0 mmol/L	Glucose <55 - 40 mg/dL; <3.0 - 2.2 mmol/L	Glucose <40 - 30 mg/dL; <2.2 - 1.7 mmol/L	Glucose <30 mg/dL; <1.7 mmol/L; life-threatening consequences; seizures	Clinical signs and symptoms are not taken into consideration for grading. Urine glucose is not graded.

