Hypokalemia	Potassium <LLN - 3.0 mmol/L	Symptomatic with Potassium <LLN - 3.0 mmol/L; intervention indicated	Potassium <3.0 - 2.5 mmol/L; hospitalization indicated	Potassium <2.5 mmol/L; life-threatening consequences	“Symptomatic” ranges are applied for grade 2, grade 1 not assigned, i.e. worst case applied. Clinical signs and symptoms are not taken into consideration for grading of grade 3 and 4.
Hypomagnesemia	Magnesium <LLN - 1.2 mg/dL; <LLN - 0.5 mmol/L	Magnesium <1.2 - 0.9 mg/dL; <0.5 - 0.4 mmol/L	Magnesium <0.9 - 0.7 mg/dL; <0.4 - 0.3 mmol/L	Magnesium <0.7 mg/dL; <0.3 mmol/L; life-threatening consequences	Clinical signs and symptoms are not taken into consideration for grading.
Hyponatremia	Sodium <LLN - 130 mmol/L	Sodium 125-129 mmol/L and asymptomatic	Sodium 125-129 mmol/L symptomatic; 120-124 mmol/L regardless of symptoms  Sodium <130-120 mmol/L	Sodium <120 mmol/L; life-threatening consequences	Clinical signs and symptoms are not taken into consideration for grading. Worst case (“<130-120 mmol/L” for grade 3 added by Janssen) is applied across grade 2/3 ranges: 120-129 mol/L assigned to grade 3, grade 2 not used.
Renal and urinary disorders					
Proteinuria	1+ proteinuria; urinary protein $\geq$ ULN - <1.0 g/24 hrs; urinary protein $\geq$ ULN - <1000 mg/day	Adult: 2+ and 3+ proteinuria; urinary protein 1.0 - <3.5 g/24 hrs;	Adult: 4+ proteinuria; urinary protein $\geq$ 3.5 g/24 hrs;	-	In case both 24-h urine collection and dipstick are collected, then worst case is taken, as opposed to having 24-h urine

CTCAE Term	Grade 1	Grade 2	Grade 3	Grade 4	Janssen implementation notes
		urinary protein 1000 - <3500 mg/day  Pediatric: Urine P/C (Protein/Creatinine) ratio 0.5 - 1.9; Urine P/C (Protein/Creatinine) 56.5 – 214.7 g/mol	urinary protein $\geq$ 3500 mg/day;  Pediatric: Urine P/C (Protein/Creatinine) ratio $>$ 1.9; Urine P/C (Protein/Creatinine) $>$ 214.7 g/mol		collection take precedence over dipstick. Added ranges in SI unit for urinary protein (mg/day) and for urine P/C (g/mol). Pediatric grading is applied to age range [0-18]. Adult grading is applied for ages [ $>$ 18].

\* Grade 0 is assigned to a lab assessment when the lab test is described in the table, but the lab value is not assigned a grade 1 or higher.

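### High glucose, neutrophils and platelets, and high WBC up to 100 x 10^9/L, share Grade 0 with normal values and cannot enter the grade 2 or higher listing

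*SAP*

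**What the plan says.** SAP Section 5.6.3.1 plans two laboratory outputs. The first is descriptive statistics of change from baseline by intervention group for selected tests; glucose, WBC, neutrophils and platelets are all named. The second is a listing of participants with toxicity grades of 2 or higher under the grading table in Section 6.9 (Appendix 10).

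That table treats the four tests as follows:

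- Glucose has one row, Hypoglycemia, whose first grade is "Glucose <LLN - 55 mg/dL; <LLN - 3.0 mmol/L". There is no row for high glucose.
- Neutrophils and platelets each have one row, for decreased counts.
- WBC has a row named "White blood cell decreased", with grades 1 to 4, and a Leukocytosis row. Leukocytosis has no grade 1 or 2; its grade 3 starts at ">100,000/mm 3 ; >100 x 10e9 /L".

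Two rules lead to Grade 0. The footnote, for values that reach no grade of 1 or higher, begins "Grade 0 is assigned to a lab assessment when the lab test is described in the table, but the lab value is not assigned". Near the top of the appendix, if a result falls in a grade band but is also inside the local normal limits, "the value is considered to be normal and will be reset to grade 0".

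In Protocol Section 9.4.3, "Common Terminology Criteria (CTC) will be used to identify abnormal laboratory test results", and their incidence and severity are to be summarized by treatment group. Protocol Section 3 and SAP Section 1.1 both list the number or proportion of participants with abnormal laboratory values as a secondary safety endpoint.

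**The concern.** The footnote is triggered by the test, not by the direction of the abnormality. Once a test has any row, every value that matches no row becomes Grade 0. For a test graded only when low, a markedly high result and a normal result get the same code, and the graded data cannot tell them apart.

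What is at stake is a stated safety endpoint. The SAP defines an abnormal laboratory result in no other way than by these grades. Anyone who takes them as the measure of abnormality, as Protocol Section 9.4.3 does, would miss every high value of glucose, neutrophils and platelets, and every high WBC up to 100 x 10^9/L. The grade 2 or higher listing is also the only planned laboratory output that identifies individual participants, and these values cannot reach it.

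**Working it through.** The plan gives no figure to reproduce, so the check applies the grading rule as written to test values.

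**Inputs (SAP Section 6.9).** Counts are in 10^9/L and glucose is in mmol/L.

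| Test | Grade 1 | Grade 2 | Grade 3 | Grade 4 | High direction |
|---|---|---|---|---|---|
| WBC | below LLN to 3.0 | <3.0 to 2.0 | <2.0 to 1.0 | <1.0 | grade 3 only, >100 |
| Neutrophils | below LLN to 1.5 | <1.5 to 1.0 | <1.0 to 0.5 | <0.5 | none |
| Platelets | below LLN to 75 | <75 to 50 | <50 to 25 | <25 | none |
| Glucose | below LLN to 3.0 | <3.0 to 2.2 | <2.2 to 1.7 | <1.7 | none |

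**Rule.** The grade is that of the row the value falls in; if it falls in none, the grade is 0. A participant is listed if the grade is 2 or higher.

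**Assumption.** The documents give no lower limits of normal (LLN). I used WBC 4.0, neutrophils 1.8, platelets 150 and glucose 3.9. The results for high values do not depend on this choice.

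**Results.**

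| Test | Value | Grade | Listed |
|---|---|---|---|
| WBC | 0.8 / 1.5 / 2.5 | 4 / 3 / 2 | yes |
| WBC | 3.5 | 1 | no |
| WBC | 7 | 0 | no |
| WBC | 15 / 30 / 60 / 100 | 0 | no |
| WBC | 100.1 | 3 | yes |
| Neutrophils | 0.4 / 0.9 / 1.2 | 4 / 3 / 2 | yes |
| Neutrophils | 4 | 0 | no |
| Neutrophils | 12 / 40 / 90 | 0 | no |
| Platelets | 20 / 60 | 4 / 2 | yes |
| Platelets | 250 | 0 | no |
| Platelets | 600 / 1500 | 0 | no |
| Glucose | 1.5 / 2.5 | 4 / 2 | yes |
| Glucose | 5 | 0 | no |
| Glucose | 9 / 15 / 30 | 0 | no |

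A WBC of 7 and one of 60 get the same grade, as do a glucose of 5 and one of 30.

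**Is the reading strained?** No. Fibrinogen is also graded on one side only, and its implementation note sends values above ULN to Grade 0 explicitly. Nor is one-sidedness a general feature of the table: hemoglobin, lymphocytes, calcium, potassium and sodium have rows in both directions.

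**Exposure.** The Part 1 schedules (Protocol Sections 1.3.1 and 1.3.3) draw hematology and chemistry at Weeks 2, 4, 8, 12 and 16, and at Weeks 20, 24, 28, 32 and 36: 5 + 5 = 10 scheduled post-baseline visits. This is an upper limit, because SAP Section 1 records that the study was terminated after the first interim analysis.

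**The case against.** The case on the other side is substantial, and much of it stands.

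- A reader might infer that the footnote keeps these values off the listing. It does not. With the footnote deleted they would still have no grade of 2 or higher. The missing rows cause the omission; the footnote adds only the shared code.
- A reader might infer that the SAP declares these highs normal. The footnote is worded as a residual category, and the reset rule is a separate route into Grade 0. The defect is that the two groups cannot be distinguished.
- A reader might infer that the highs vanish from the report. SAP Section 5.6 requires minimum and maximum for continuous safety variables, so an extreme rise would generally show in its group's statistics. Protocol Section 8.2.4 has the investigator review laboratory results and record clinically relevant changes as adverse events, which SAP Section 5.6.2 summarizes. For the same reason, although Protocol Section 2.3 names infections as a bermekimab risk, the documents do not support saying that infections would be missed.
- A reader might infer that a planned grade-based count would be too low. SAP Section 5.6.3.1 plans no such count, and Section 6.2 (Appendix 2) says the safety analyses are reduced.
- It would be wrong to say that every WBC up to 100 x 10^9/L is Grade 0. Low WBC is graded, and values below 3.0 x 10^9/L are listed.
- The table is said to be based on CTCAE v5.0. Whether the missing rows follow that source cannot be checked from these documents, so no departure from it is claimed.

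What the objection does not remove is the gap in the endpoint. A group maximum names no participant, gives no count and is not related to ULN. Adverse event recording depends on the investigator judging the change clinically relevant.

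**Conclusion.** The point holds as a minor one. Under the written table, high glucose, neutrophils and platelets, and WBC from above ULN to 100 x 10^9/L, share Grade 0 with normal values and cannot enter the grade 2 or higher listing. Grades alone would therefore not identify these abnormalities, although the protocol uses them for that purpose and the proportion of participants with abnormal laboratory values is a secondary endpoint. The values would show only in group change-from-baseline statistics or through an investigator's adverse event record.

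The size is four analytes named in SAP Section 5.6.3.1, at up to ten scheduled post-baseline visits in Part 1. The number of participants affected is unknown, since the documents give no expected frequency; the values tested above are illustrations. The conclusion rests on applying the footnote as written, which the fibrinogen note supports. It does not touch the efficacy analyses.

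**What to change.** In SAP Section 6.9, reword the footnote so that an out-of-range value on a side the table does not grade is coded 'not graded (high)' or 'not graded (low)' instead of Grade 0.

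The new code alone will not bring any participant into view. So in Section 5.6.3.1 add, by arm, the number and percentage of participants who are normal or low at baseline and above ULN at any post-baseline visit, for glucose, WBC, neutrophils and platelets. Identify those participants in a listing kept apart from the grade 2 or higher listing. Mixing the two would let small excursions crowd out graded toxicity.

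This uses the existing laboratory reference ranges, sets no new clinical threshold and needs no new data. The cost is a few sentences, minor programming, and one extra small table and listing. The listing will include some trivial excursions. A participant already above ULN at baseline who rises further will not be counted as a shift.
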